5.0 STUDY SCHEMATIC

	Visit 1	Visit 2	Visit 3	Visit 4
Day	1	14 ± 2	29 ± 2	42 ± 4
Procedures	Screening/ Enrollment Before 12 pm	Interim Visit	End of Study/Early Termination Before 12 pm	Telephone Follow-Up Visit
Informed Consent	X			
Medical History and Demographics	X			
Vital Signs	X	X	X	
Pregnancy Test*	X	X	X	
Physical Exam	X		X	
HEENT Exam	X	X	X	
% Scalp Affected	X	X	X	
Investigator Global Assessment	X	X	X	
Concomitant Medication	X	X	X	X
Laboratory Evaluations	X		X	
Cortisol Response Test	X		X	
Confirm Inc/Exc Criteria	X			
Dispense Wristband	X			
Weigh and Dispense Study Product	X	X		
Collect and Weigh Study Product		X	X	
Dispense/Review Patient Diary	X	X	X	
Ocular Assessment		X	X	
Adverse Events		X	X	X
Evaluation of Patient Compliance to the Protocol		X	X	

* Pregnancy test will be carried out for females of childbearing potential.

CONFIDENTIAL PROTOCOL

An Open Label, Safety Study to Assess the Potential for Adrenal Suppression Following Maximal Use Treatment with Desoximetasone 0.25% shampoo(Taro Pharmaceuticals U.S.A., Inc.) in Patients with Scalp Psoriasis

6.0 LIST OF ABBREVIATIONS AND TERMS

Abbreviation	Term
ADL	Activities for Daily Living
ADR	Adverse Drug Reaction
AE	Adverse Event
BP	Blood Pressure
C	Celsius
CRF	Case Report Form
CRO	Clinical Research Organization
eCTD	electronic Common Technical Document
FDA	Food and Drug Administration
HR	Heart Rate
HRT	Hormone Replacement Therapy
ICF	Informed Consent Form
ICH	International Conference on Harmonization
IGA	Investigator's Global Assessment
IND	Investigational New Drug
IRB	Institutional Review Board
ITT	Intent-to-Treat
IUD	Intrauterine Device
LOCF	Last Observation Carried Forward
ml	Milliliter
mITT	Modified Intent-to-Treat
NDA	New Drug Application
NSAID	Non-Steroidal Anti-Inflammatory Drug
OHRP	Office of Human Rights Protection
OTC	Over-the-Counter
PUVA	Psoralen and UltraViolet A
RR	Respiratory Rate
SAE	Serious Adverse Event
SAP	Statistical Analysis Plan
USA	United States of America

CONFIDENTIAL PROTOCOL

An Open Label, Safety Study to Assess the Potential for Adrenal Suppression Following Maximal Use Treatment with Desoximetasone 0.25% shampoo(Taro Pharmaceuticals U.S.A., Inc.) in Patients with Scalp Psoriasis

7.0 INTRODUCTION

Taro Pharmaceuticals U.S.A., Inc. (Taro) plans to submit an Investigational New Drug Application (IND) for a new formulation of desoximetasone: desoximetasone 0.25% shampoo. This product contains a potent corticosteroid to be indicated for the treatment of patients with moderate to severe psoriasis.

7.1 Disease Being Treated

Psoriasis is an immune (T-cell)-mediated inflammatory skin disease that affects approximately 2% of the western population.¹ The most common type of psoriasis in both adults and children is plaque psoriasis, which is characterized by the presence of raised, thickened red lesions that are covered by silvery white scales, most commonly seen on the knees and/or elbows. Although there are reports implicating a genetic association with the disease, there are also studies that have established a set of psoriasis triggers including stress, medications (such as lithium, antimalarials, indomethacin, quinidine, beta blockers), injury or infection. The condition is considered chronic although the frequency and severity of outbreak in an individual can fluctuate without apparent cause.¹⁻³

At least 50% of all psoriasis cases have scalp psoriasis. Although head represents only 10% of the whole body surface, the visibility and symptoms of scalp psoriasis can be seriously debilitating for many patients, inducing social and emotional distress and negatively impacting quality of life.⁴ Scalp psoriasis is more difficult to treat compared to psoriasis of the body, because the skin of the scalp is less accessible to topical treatments primarily because of the presence of hair. Moreover, vehicles used in psoriasis medications are often not cosmetically acceptable for scalp treatment, thereby negatively impacting treatment adherence. There is a need for effective, safe and cosmetically acceptable products for the treatment of scalp psoriasis to improve both compliance and response to treatment.⁵

7.2 Availability and Efficacy of Already Approved Therapies

Treatment of plaque psoriasis depends on the severity of the condition, previous treatment regimens and personal preference of the patient. Scalp psoriasis treatments historically include topical creams, sprays, lotions, foams, and the more recently introduced shampoos. Examples of marketed products include corticosteroids (Topicort[®], Clobex[™]), Vitamin A and D derivatives (Tazorac[®], Dovonex[®]), NSAIDs (salicylic acid), etc. For more severe cases, systemic therapy (methotrexate, oral retinoids, UV light, biologics, etc) may be warranted; however, the side effect profile of these products limits their use.^{1,2,5-7}

Desoximetasone is a high potency synthetic corticosteroid marketed in a number of formulations: gel (0.05%), cream (0.05% and 0.25%), and ointment (0.05% and 0.25%). All these formulations are encompassed under the Topicort[®] brand, acquired by Taro Pharmaceuticals U.S.A., Inc. (Taro) in 2004. Most recently, Taro received approval on April 11, 2013 for a new dosage form (spray) under NDA #204141, Topicort[®] (desoximetasone) Spray, 0.25%, a super high potency formulation that is indicated for the treatment of plaque psoriasis in patients 18 years of age or older.⁸ Topical application of high potency steroids at the recommended dosing levels are usually well tolerated in all populations, with less than 2% of patients reporting adverse reactions (7% in the pediatric population). The most commonly reported adverse events are burning, stinging, pruritus, and skin thinning/atrophy.^{1,2,5-7}

CONFIDENTIAL PROTOCOL

An Open Label, Safety Study to Assess the Potential for Adrenal Suppression Following Maximal Use Treatment with Desoximetasone 0.25% shampoo(Taro Pharmaceuticals U.S.A., Inc.) in Patients with Scalp Psoriasis

Shampoos are considered a preferred treatment option for scalp psoriasis because of ease of application and cosmetic acceptability. There are many OTC coal tar shampoos in the market for treating mild scalp psoriasis. For the moderate-severe cases, a prescription shampoo containing potent corticosteroids is available in the market (Clobex™ shampoo, clobetasol propionate, 0.05%).

A new formulation of desoximetasone (desoximetasone 0.25% shampoo) has been developed by Taro Pharmaceuticals U.S.A., Inc. (Taro), and is the Test product used in this study

7.3 Scientific and Statistical Considerations

In some instances high potency steroids applied topically have been known to cause suppression of the hypothalamic-pituitary-adrenal (HPA) axis. In order to assess HPA axis function plasma levels of cortisol are measured before (basal) and after a bolus administration of synthetic α 1-24-adrenocorticotropic hormone (ACTH). In this study Cortrosyn™ (cosyntropin, a synthetic subunit of ACTH) (Amphstar Pharmaceuticals, Inc.) will be used according to manufacturer instructions to assess HPA axis function (See Appendices D, E).⁹ Recovery from steroid-induced adrenal insufficiency is usually rapid after the treatment is withdrawn.¹⁰ See Appendix D for further explanation of the evaluation of the role of topical corticosteroids in HPA axis suppression.

Taro Pharmaceuticals USA has recently completed an open label safety and efficacy study to assess adrenal suppression in adults with moderate to severe plaque psoriasis after 4 weeks of treatment under maximal use conditions with the test product, desoximetasone 0.25% spray. Of 21 evaluable subjects, adrenal suppression was identified in 1 of 12 subjects having involvement of 10-15% of body surface area (BSA) and 2 of 9 subjects having involvement of > 15% of BSA after treatment with Topicort® Topical Spray twice a day for 28 days. Adrenal function returned to normal at the first follow-up visit, which was 28 days after the end of treatment, for all 3 of these patients¹¹

This study design is based on similar studies performed, submitted and accepted by the FDA for recently approved high potency spray and foam topical corticosteroid formulations, topical corticosteroid/topical vitamin D3 analogue combination agents, and recommendations from the FDA in IND 101789 Guidance Meeting that took place on 01/14/2015 and an FDA Advice Letter dated 04/27/2015 (Reference ID: 3740601) for desoximetasone 0.15% topical spray, and recommendations provided by the FDA in the Meeting Request – Written Reponses Letter dated 09/18/2013 for PIND 118881 (Reference ID 3374240) for desoximetasone 0.25% shampoo.^{9,12-15}

7.4 Risks and Benefits

Known adverse reactions to topical corticosteroids include burning, itching, irritation, dryness, folliculitis, hypertrichosis, acneiform eruptions, hypopigmentation, perioral dermatitis, allergic contact dermatitis, maceration of the skin, secondary infection, skin atrophy, striae and milia. Dosing for extended periods of time may result in suppression of adrenal function.

Cortrosyn™ for injection is intended diagnostic and not therapeutic use and adverse reactions other than a rare hypersensitivity reaction are not anticipated. Known reactions are slight whealing with erythema at the site of injection.

The subject may benefit from clearing of the lesions and improvement of the condition of the disease. If the drug is approved, then many patients may benefit from its use.

CONFIDENTIAL PROTOCOL

An Open Label, Safety Study to Assess the Potential for Adrenal Suppression Following Maximal Use Treatment with Desoximetasone 0.25% shampoo(Taro Pharmaceuticals U.S.A., Inc.) in Patients with Scalp Psoriasis

The potential risks and benefits of participation in the study will be explained to the patient verbally and written in the informed consent form.

All patients enrolled in this study will receive the benefit of free specialized medical care, beyond standard medical treatment that would be expected through most health insurance plans. In addition, the patient will receive a stipend as compensation for time and inconvenience related to study participation including costs associated with travel to and from the medical facility.

Ethical consideration related to this protocol and the use of human patients will be reviewed by an IRB.

8.0 STUDY OBJECTIVES

The objectives of this study are to:

1. Evaluate the potential of desoximetasone 0.25% shampoo to suppress HPA axis function in patients with moderate to severe scalp psoriasis.
2. Evaluate the efficacy parameters and adverse event (AE) profiles of desoximetasone 0.25% shampoo administered to patients with moderate to severe scalp psoriasis.

9.0 INVESTIGATIONAL PLAN

9.1 Study Design and Plan Description

This open-label, safety study is designed to evaluate the potential for adrenal suppression after maximal use treatment with desoximetasone 0.25% shampoo (Taro Pharmaceuticals, U.S.A.), for the treatment of moderate to severe scalp psoriasis.

Up to 40 eligible patients with stable plaque psoriasis of the scalp that satisfy all eligibility criteria will be enrolled into the study at Visit 1 to obtain 20 evaluable patients. Patients must be overall in good health. They should have a current diagnosis of moderate to severe scalp psoriasis with IGA score of at least 3 or 4.

Up to 40 patients will be enrolled to obtain 20 evaluable patients with a confirmed diagnosis of moderate to severe scalp psoriasis.

Patients enrolled in the study will apply product once daily for 28 days, according to provided instructions. Each patient is expected to receive 28 doses of study product.

Patients will attend a total of 3 Clinic Visits and a telephone follow-up phone call (Visit 4) as follows:

- **Visit 1 (Day 1):** Screening/Enrollment
- **Visit 2 (Day 14±2):** Interim Visit
- **Visit 3 (Day 29 ± 2):** End of Study or Early Termination
- **Visit 4 (Day 42± 4):** Follow-Up Telephone Phone Call

The primary endpoint is the proportion of patients in the study with HPA axis suppression following treatment with the study medication.

The safety profile of each treatment group will be evaluated by comparing adverse events.

Ethical consideration related to this protocol and the use of human patients will be reviewed by an IRB.

CONFIDENTIAL PROTOCOL

An Open Label, Safety Study to Assess the Potential for Adrenal Suppression Following Maximal Use Treatment with Desoximetasone 0.25% shampoo(Taro Pharmaceuticals U.S.A., Inc.) in Patients with Scalp Psoriasis

9.2 Selection of Study Design

This study design is based on similar studies performed, submitted and accepted by the FDA for recently approved high potency spray and foam topical corticosteroid formulations, topical corticosteroid/topical vitamin D3 analogue combination agents, and recommendations from the FDA in IND 101789 Guidance Meeting that took place on 01/14/2015 and an FDA Advice Letter dated 04/27/2015 (Reference ID: 3740601) for desoximetasone 0.15% topical spray, and recommendations provided by the FDA in the Meeting Request – Written Reponses Letter dated 09/18/2013 for PIND 118881 (Reference ID 3374240) for desoximetasone 0.25% shampoo.^{9,12-15}

9.3 Selection of Study Population

9.3.1 Inclusion Criteria

1. Male or non-pregnant, non-lactating females 18 years of age or older.
2. If female and of childbearing potential, prepared to abstain from sexual intercourse or use a reliable method of contraception during the study (e.g., condom, IUD, oral, transdermal or injected hormonal contraceptives). Female patients using hormonal contraceptives should have been on the same product/dosing regimen for at least 28 days before baseline and should not change this regimen during the study.
3. IRB-approved, signed informed consent form that meets all criteria of current FDA regulations.
4. Patients with a confirmed clinical diagnosis of stable plaque psoriasis of the scalp with $\geq 25\%$ scalp affected.
5. Investigator Global Assessment (IGA) score of 3 (Moderate) or 4(Severe)

9.3.2 Exclusion Criteria

1. Females who are pregnant, nursing, planning to become pregnant during the duration of the study, or if of child-bearing potential and sexually active and not prepared to use appropriate contraceptive methods to avoid pregnancy.
2. Patients < 18 years of age.
3. Patients whose scalp psoriasis necessitates systemic or other concomitant topical therapies during the study. Concomitant treatment of body psoriasis with OTC topical products, including emollients, is allowed.
4. IGA score < 3 .
5. Scalp psoriasis with $< 25\%$ scalp affected.
6. History of psoriasis that has been unresponsive to topical corticosteroid therapy.
7. Patient has a scalp skin condition that would interfere with the diagnosis or assessment of plaque psoriasis of the scalp (e.g., seborrheic dermatitis, eczema, cutaneous T-cell lymphoma, or other forms of psoriasis including guttate, inverse, pustular or erythrodermic psoriasis).
8. History of an adverse reaction to CortrosynTM or similar test reagents

CONFIDENTIAL PROTOCOL

An Open Label, Safety Study to Assess the Potential for Adrenal Suppression Following Maximal Use Treatment with Desoximetasone 0.25% shampoo(Taro Pharmaceuticals U.S.A., Inc.) in Patients with Scalp Psoriasis

9. Presence of pigmentation, extensive scarring, pigmented lesions, or sunburn in the treatment areas that could interfere with the rating of efficacy parameters, including planned extensive exposure to sunlight during the study.
10. History of allergy or sensitivity to corticosteroids or history of any drug hypersensitivity or intolerance which, in the opinion of the Investigator, would compromise the safety of the patient or the results of the study.
11. Patient has a significant history or current evidence of chronic infectious disease, system disorder, organ disorder or insufficiency, immunosuppression (from medical treatment or disease), organ transplant or other medical condition that, in the Investigator's opinion, would place the study patient at undue risk by participation in the study.
12. Patient is currently receiving or has received any radiation therapy or anti-neoplastic agents within 3 months before baseline.
13. Known history of hypothalamic-pituitary-adrenal axis impairment or any other disturbance of the adrenal function (e.g. Cushing or Addison disease).
14. Known or suspected severe renal insufficiency or severe hepatic disorders or severe heart disease.
15. Patients who have a history of or current diagnosis of glaucoma or posterior subcapsular cataracts or any other ocular condition that, in the opinion of the Investigator, would place study patient at undue risk.
16. Patients who have had surgery on the eyes or eyelids within 1 month before baseline or plan to have eye or eyelid surgery during the study.
17. Patients with active infection (including but not limited to bacterial, fungal and viral infection) and/or open wounds on the entire head and neck area.
18. Use within 4 weeks before baseline of 1) oral or intravenous corticosteroids, 2) UVA/UVB therapy, 3) PUVA (psoralen plus ultraviolet A therapy, 4) topical tacrolimus, 5) topical pimecrolimus, 6) systemic retinoids or 7) any other systemic psoriasis treatment
19. Use of tanning booths or nonprescription UV light source within 2 weeks before baseline.
20. Use within 8 weeks before baseline of 1) immunomodulators or immunosuppressive therapies or 2) interferon.
21. Use within 14 days before baseline of calcipotriene or other Vitamin D preparations.
22. Changed brands/types or frequency of use of routine hair care products (shampoo, conditioner, sprays etc.) within 14 days before baseline, or intend to change during the study.
23. Use of systemic antibiotics or prescription-strength systemic anti-inflammatory agents within 1 month before baseline.
24. Use of the following within 2 weeks before baseline:
 - a. Topical anti-psoriatic agents.
 - b. Topical corticosteroids.

CONFIDENTIAL PROTOCOL

An Open Label, Safety Study to Assess the Potential for Adrenal Suppression Following Maximal Use Treatment with Desoximetasone 0.25% shampoo(Taro Pharmaceuticals U.S.A., Inc.) in Patients with Scalp Psoriasis

- c. Topical retinoids.
- d. Topical anti-inflammatory agents.
- e. Medicated shampoos for scalp psoriasis (including coal tar shampoo).
- f. New regimens of beta blockers.
- g. Lithium preparations.
- h. Anti-malarial agents.

25. Patient has been treated within 12 weeks before baseline with any biological therapies for psoriasis.

26. Inability to understand the protocol requirements, instructions, and study-related restrictions, the nature, scope, and possible consequences of the clinical study.

27. Unlikely to comply with the protocol requirements, instructions, and study-related restrictions, such as uncooperative attitude, inability to return for follow-up visits, and improbability of completing the clinical study.

28. Receipt of any drug as part of a research study within 30 days before baseline.

29. The patient is a member of the investigational study staff or a member of the family of the investigational study staff.

30. Previous participation in this study.

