9.3.3 Restrictions during the Study

The following concomitant medications will not be allowed while enrolled in the study:

Restricted medication	Examples (not comprehensive)	Wash out
Topical corticosteroids (on scalp or body), retinoids or anti-inflammatory agents (on scalp)	Topicort® (desoximetasone 0.25%) spray, Cortaid® (hydrocortisone 1%), Clobex® (clobetasol 0.05%), Diprolene® (betamethasone 0.05%), retinol, diclofenac, etc.	2 weeks
Topical anti-psoriatic medication (on scalp)	Psorcon® ointment/cream, Dovonex® (calcipotriene), Tazorec® (tazarotene), Vectical® (calcitriol), salicylic acid, anthralin, coal tar, etc., including medicated shampoos	2 weeks
Beta blockers, lithium preparations, anti-malarial agents or tanning booths	metoprolol, labetalol, Eskalith, Lithobid, quinine, etc.	2 weeks

CONFIDENTIAL PROTOCOL

An Open Label, Safety Study to Assess the Potential for Adrenal Suppression Following Maximal Use Treatment with Desoximetasone 0.25% shampoo(Taro Pharmaceuticals U.S.A., Inc.) in Patients with Scalp Psoriasis

Biologic treatment for psoriasis	Remicade® (infliximab), Enbrel® (etanercept), Humira® (adalimumab), etc.	12 weeks
Chemotherapy Radiation therapy		3 months
Systemic corticosteroids Systemic antipsoriatic treatment Systemic antibiotics PUVA therapy UVB therapy Prescription strength systemic anti-inflammatory agents	Prednisone (Short and occasional use of intranasal, inhaled or ophthalmic corticosteroids for acute and transitory conditions [e.g. allergic rhinitis] up to 1 mg per day is acceptable) methotrexate, cyclosporine, hydroxyurea *the use of acetylsalicylic acid for prophylactic use up to 325 mg/day is allowed, provided that the patient is on a stable dose for at least 3 months and the regimen will remain constant throughout the study	4 weeks
Systemic retinoids	Soriatane® (acitretin), Isotretinoin etc	4 weeks
Systemic immunosuppressive drugs	tacrolimus, pimecrolimus	8 weeks

Patients and will be advised to avoid environmental conditions that may exacerbate their disease state. Patients will be advised to avoid exposure to sunlight of a duration that would require application of sunscreen.

In addition, patients must have consistently used a single brand/type of hair care product (e.g., shampoo, conditioner, spray, etc.) for a minimum of 14 days prior to baseline. Patients will be asked to continue using the same brand/type and frequency of use throughout the study.

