Patients will be questioned about all concomitant prescription and OTC medication use at each study visit. All concomitant medications will be recorded in the patient's study chart. Any patient who violates any of the listed restrictions should be dropped from continued participation in the study by the Investigator.

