10.1.1 Determination of Sample Size

The sample size of 20 evaluable patients was deemed appropriate to meet the objective of the study.

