## **6.2 Statistical Analyses**

### **6.2.1 Safety Analysis of Potential HPA Axis Suppression**

Dosing will be once daily for 28 days. Patients who have normal adrenal function at baseline, use at least 21 doses of the study product and have data from a post-treatment cortisol response test will be included in the analysis.

The primary analysis of interest is to assess the proportion of patients considered to have demonstrated possible HPA axis suppression following treatment with the study medication.

A logistic regression of the proportion of patients in the study with HPA axis suppression may be performed as exploratory analysis with % scalp affected as a covariate. This will depend on the distribution of the % scalp data collected. See Appendix D for results from the cortisol response test considered indicative of potential HPA axis suppression.

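### Exclusion 3 and Section 9.3.3 give conflicting answers on an over-the-counter (OTC) corticosteroid used on the body during the study, and the HPA analysis would not identify such patients

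*Protocol*

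**What the plan says.** Protocol Section 9.3.2, exclusion 3, excludes patients whose scalp psoriasis needs systemic or other topical therapy. It then adds: "Concomitant treatment of body psoriasis with OTC topical products, including emollients, is allowed". The synopsis repeats the sentence.

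Protocol Section 9.3.3 opens its table with "The following concomitant medications will not be allowed while enrolled in the study". The first row reads "Topical corticosteroids (on scalp or body), retinoids or anti-inflammatory agents (on scalp"), and one of its named examples is "Cortaid® (hydrocortisone 1"%). After the table: "Any patient who violates any of the listed restrictions should be dropped from continued participation in the study by the Investigator".

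Section 9.1 defines the outcome: "The primary endpoint is the proportion of patients in the study with HPA axis suppression following treatment with the study medication". SAP Section 6.2.1 takes into the HPA analysis those with "normal adrenal function at baseline, use at least 21 doses of the study product and have data from a post-treatment cortisol response test". Protocol Section 10.1.2 sets the same three conditions.

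**The concern.** Read literally, exclusion 3 lets a patient treat body plaques with any OTC topical, including a corticosteroid if one is sold that way. Section 9.3.3 would have the same patient dropped. Two sites could each follow a sentence of the protocol and handle the same patient differently.

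The study exists to measure adrenal suppression. Protocol Appendix E itself says that exogenous corticosteroids absorbed through the skin may act on the axis. With one open-label arm, there is no comparator against which to separate a second steroid's contribution from that of the shampoo. A suppressed patient who also used another corticosteroid would be counted as a case following study medication, and the main table would not show the difference.

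**Working it through.** The plan has no figure to reproduce here. On size it says only: "The sample size of 20 evaluable patients was deemed appropriate to meet the objective of the study". The check is therefore a comparison of texts, followed by simple arithmetic for scale.

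**1. The rules side by side**

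| Text | Corticosteroid on the body | OTC status mentioned? | Refers to the other rule? |
|---|---|---|---|
| Exclusion 3 and synopsis | Not excepted from the permission | Yes | No |
| Section 9.3.3, first row | Barred while enrolled | No | No |

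**2. Does other text settle it?**
- *Site qualifiers in Section 9.3.3.* Corticosteroids are barred on scalp or body, while topical retinoids, anti-inflammatory agents and anti-psoriatic products are barred on the scalp only. This suggests how the two rules may be meant to fit together, but the protocol does not say so.
- *Exclusion 24b.* Topical corticosteroid use in the 2 weeks before baseline excludes a patient. This limits the question to patients who start or resume use on study. It does not govern that use.
- *Named example.* The documents do not say that hydrocortisone 1% is OTC. If it is, the conflict attaches to a named product. If it is not, the conflict remains for any OTC topical corticosteroid.

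**3. Following a user into the analysis**
- The three conditions in SAP 6.2.1 and Protocol 10.1.2 concern the baseline test, the number of doses and the post-treatment test. None concerns other corticosteroids, so a user who meets them is counted.
- The cortisol listing (L16.2.6.1) has no column for other corticosteroid use.
- The deviation table (T16.1.9.2) has a line for restricted medication. A site relying on exclusion 3 would have no reason to record a deviation.
- If a site applies the drop rule, timing matters. Use found at Visit 2 (Day 14 ± 2, so Day 16 at the latest) leaves at most 16 scheduled once-daily doses. That is below 21, so the patient leaves the HPA set. Use found only at Visit 3 comes after treatment has ended, and the patient can still qualify.

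**4. Scale with n = 20 evaluable**

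Proportion = x/n, with exact (Clopper-Pearson) two-sided 95% intervals.

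| Result | Proportion | 95% interval |
|---|---|---|
| 0/20 | 0% | 0 to 16.8% |
| 1/20 | 5% | 0.1 to 24.9% |
| 2/20 | 10% | 1.2 to 31.7% |

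- One patient's status changed by another steroid: 1/20 − 0/20 = 5.0 points.
- One suppressed patient lost: 1/20 to 0/19, a fall of 5.0 points.
- One non-suppressed patient lost, no cases: 0/20 to 0/19, no change.
- One non-suppressed patient lost, one case: 1/20 = 5.0% to 1/19 = 5.3%, about 0.3 points.
- A user whose classification does not change: no change.

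**The case against.** The strongest reply is that Section 9.3.3 is the on-study medication rule, that it bars body corticosteroids by class, and that it adds a consequence. The sentence in exclusion 3 only clarifies who is excluded for needing other therapy. On that view the site qualifiers show that the two texts work together, and exclusion 24b shows the same intent before baseline. This has weight. A reader might infer that the protocol simply leaves a second steroid source open, and the documents do not support that: the table restricts it. What remains is that exclusion 3 is the only text that speaks of OTC treatment of body psoriasis, so it can equally be read as the specific rule, and no precedence is stated.

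A reader might also infer that every confounded or lost patient shifts the result by 5 points. That is not so. The figure applies when a patient's status changes or a suppressed patient is lost.

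Nor does dropping a patient always lose the data. Section 9.3.4 asks for end-of-study procedures on early discontinuation, and a patient with 21 doses and a valid test still qualifies. Enrolment of up to 40 to obtain 20 evaluable also gives some room, although Section 9.3.4 says withdrawn patients are not replaced.

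Finally, OTC medication is already asked about at each visit, and SAP listing L16.2.4.3 shows product, route, location and dates. No new data collection is needed. The missing piece is the link from those data to the HPA result.

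**Conclusion.** Wrong as written, in that the rules contradict each other; minor to moderate in importance. Exclusion 3 and Section 9.3.3 do not give one answer for an OTC corticosteroid begun or resumed on the body during the study, and neither the HPA analysis set nor the cortisol listing would identify a patient who used one.

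The possible effect is 5 points on the primary proportion for each patient whose suppression status another steroid changes. How many patients that could be is unknown: the documents give neither the frequency of such use nor the systemic absorption from it, so the actual effect may be nil. The conclusion rests on at least one topical corticosteroid being available OTC. That hydrocortisone 1% is such a product is an assumption. No view is taken on which clinical rule is right.

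**What to change.** **Protocol.** Reconcile exclusion 3, its copy in the synopsis, and the first row of the Section 9.3.3 table so that they give one answer for OTC corticosteroids on the body, with a cross-reference. The medical team decides the content. The cost is one clause in each place.

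**SAP.** In Section 6.2.1, state how patients with on-study use of a non-study corticosteroid are handled. Add a flag to L16.2.6.1, derived from the concomitant medication data already collected. Show the route as well, because Section 9.3.3 accepts limited intranasal, inhaled or ophthalmic corticosteroid use. Report the primary proportion with and without the flagged patients. The cost is one derived column and one extra line in T16.1.9.4. This step remains useful even if enrolment has finished.
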